8.2 Rationale

8.2.1 Rationale for this Study and Study Design

When developing new drugs for clinical indications, it is necessary to collect data on the safety, tolerability, and PK in order to support further development of the compound as a useful clinical candidate and determine dose levels and dose intervals for subsequent studies. This study will assess the safety, tolerability, and PK of LOXO-292 in healthy subjects at higher dose levels than previously administrated in this population so as to ascertain the therapeutic and supratherapeutic exposures of LOXO-292 for the upcoming thorough QT study.

8.2.2 Rationale for the Dose Selection and Dose Regimen

Single doses of 160 mg are currently being investigated in 2 studies in healthy volunteers in which Cmax have been preliminarily determined. LOXO-RET-18014 is a drug-drug interaction study evaluating the effects of itraconazole and rifampin on the PK of LOXO-292. In LOXO-RET-18015 the effects of food and of a proton-pump inhibitor (omeprazole) are being evaluated on the PK of LOXO-292. Preliminary Cmax data was reported for LOXO-292 following each study part and data when LOXO-292 was administered alone under fasted conditions in these studies are presented in [Table 1](#) (Data on file at the time of protocol development).

Table 1: Maximum concentration (Cmax) values following single dose LOXO-292 (160 mg) administered under fasting conditions

LOXO-292 Study Number	Part	Sample Size (n)	Cmax* (ng/mL)
LOXO-RET-18014	1	12	1656 ± 626 ng/mL
LOXO-RET-18014	2	12	1458 ± 626 ng/mL
LOXO-RET-18015	1	20	2223 ± 685 ng/mL

*Arithmetic mean (AM) ± standard deviation (SD)
Cmax = Maximum concentration (preliminary data), mL = milliliter, ng = nanogram

Single doses of greater than 160 mg have not been given to healthy subjects and the data from [Table 1](#) suggest the single-dose Cmax average value following dose level of 160 mg LOXO-292 is approximately 1800 ng/mL.

In a dose-exposure analysis in cancer patients who received doses of 20 mg once daily to 240 mg BID in the ongoing Phase 1/2 LOXO-RET-17001 Study, the CL/F of LOXO-292 decreased with increasing dose strength leading to greater than proportional increases in LOXO-292 exposure with increases in LOXO-292 doses. The steady-state Cmax of LOXO-292 in cancer patients treated with 160 mg BID, the currently recommended Phase 2 dose and dose planned for commercialization, is 3320 ± 1220 ng/mL (n=65, [Investigator's Brochure, Version 4, October 2018](#)). Based on the data from a single dose of 160 mg when administered to healthy subjects, the Cmax of a single dose of 320 mg (the dose selected for Cohort 1) is expected to be twice as high as from 160 mg i.e., approximately 3600 ng/mL, representing the therapeutic Cmax value expected in patients. The dose of 640 mg was selected for Cohort 2 as with linear PK, it is anticipated to produce a Cmax of approximately 6640 ng/mL, which is approximately twice as high as the Cmax seen in cancer patients treated with 160 mg BID LOXO-292 and would be considered the supratherapeutic exposure target.

All AEs reported following LOXO-292 administration in LOXO-RET-18014 were \leq Grade 2 in severity and not considered related to LOXO-292. The majority of AEs reported in LOXO-RET-18015 were \leq Grade 2 in severity. There was one Grade 3 event of hypertriglyceridemia reported during the study and considered treatment related. Other LOXO-292 related events in this study included Grade 1 increased alkaline phosphatase (ALP), Grade 2 increased serum amylase, Grade 1 increased alanine aminotransferase (ALT), Grade 1 increased aspartate aminotransferase (AST), and Grade 1 dyspepsia (Data on file at the time of protocol development).

8.2.3 Rationale for Primary Endpoints

The primary endpoint of this study is to assess the safety and tolerability of LOXO-292. LOXO-292 has already been administered to healthy subjects (LOXO-RET-18014 and LOXO-RET-18015) at a single dose level of 160 mg. As a dose-exposure analysis in cancer patients (LOXO-RET-17001) indicated that a reduction in clearance led to greater than proportional increases in LOXO-292 exposure with increases in LOXO-292 doses, this study

will investigate the safety and tolerability of higher doses (i.e., potential therapeutic and supratherapeutic doses) of LOXO-292 when administered to healthy subjects. Ascending doses up to and possibly including 720 mg will be investigated. The safety endpoints in the study are deemed adequate to detect any safety signals when these higher doses of LOXO-292 are administered to healthy subjects.

8.3 Risks and/or Benefits to Subjects

The doses of LOXO-292 administered in this study are not anticipated to induce any significant risk or benefit to subjects participating in this study. The dose escalation procedures and safety monitoring practices employed by this protocol (i.e., 12-lead ECG, vital signs, clinical laboratory tests, AE monitoring, and physical examination) are adequate to protect the subjects' safety.

There will be no direct health benefit for study participants from receipt of study drug. An indirect health benefit to the healthy subjects enrolled in this study is the free medical tests received at Screening and during the study.

9 OBJECTIVES AND ENDPOINTS

9.1 Objectives

Primary:

To assess the safety and tolerability of single oral doses of LOXO-292 when administered to healthy adult subjects.

Secondary:

To assess the PK of single oral doses of LOXO-292 when administered to healthy adult subjects.

9.2 Endpoints

Safety:

Safety endpoints will include AEs including the subject incidence, number, and severity of TEAEs following single oral doses of LOXO-292 in healthy adult subjects and safety markers for 12-lead ECGs, physical examinations, vital signs, and clinical laboratory tests.

Pharmacokinetics:

The plasma PK endpoints will include AUC0-t, AUC0-24, AUC0-inf, AUC%extrap, CL/F, Cmax, Tmax, Kel, t_{1/2}, and Vz/F.

10 STUDY DESIGN

10.1 Overall Study Design and Plan

This is a Phase I, safety, tolerability, and PK SAD study.

Screening of subjects will occur within 28 days prior to dosing.

The study is planned to enrol up to 18 healthy, adult male and female (of non-childbearing potential only) subjects. Every attempt will be made to enrol at least 1 female in each cohort.

Up to 3 cohorts are planned for evaluation. In each cohort, 6 healthy adult subjects are planned for evaluation. Subjects will participate in only one cohort. In each cohort, subjects will receive a single oral dose of LOXO-292 on Day 1. Cohort 2 and possibly Cohort 3 will include a sentinel group of 2 subjects who will be dosed at least 48 hours before the remaining 4 subjects. Blood samples will be collected for the PK assessment of LOXO-292 in plasma for 168 hours postdose.

Safety and tolerability will be assessed through EOT or ET by monitoring AEs, performing physical examinations, and clinical laboratory tests, measuring vital signs, and recording ECGs.

Dose escalation to a higher dose level (i.e., next cohort) will not take place until the PI and the Sponsor have reviewed all pertinent safety/tolerability data (e.g., physical examinations, ECGs, vital signs, clinical laboratory tests, and AEs) through a minimum of 48 hours (Day 3) postdose for Cohort 1 and through a minimum of 120 hours postdose (Day 5) for Cohort 2 and have determined that adequate safety and tolerability from the previous, lower dose, cohort has been demonstrated to permit proceeding to the next cohort. Bioanalytical data, if available, may be used to guide the dose-escalation decision.

Timing of all study procedures are indicated in the Study Events Flow Chart ([Section 6](#)).

Subjects may be replaced at the discretion of the Sponsor.

10.1.1 Confinement, Return Visits, and Follow-Up

Subjects will be housed in the CRU through EOT or ET beginning on Day -1, at the time indicated by the CRU, until after completion of study procedures on Day 8 (EOT) or ET study procedures. EOT is defined as the day on which the subject is released from the CRU, following all study procedures (see Study Events Flow Chart, [Section 6](#)). Vital signs, ECG, clinical safety laboratory results, and AEs are to be available for review by the PI or designee prior to release from the CRU at EOT or ET. At all times, a subject may be required to remain at the CRU for longer at the discretion of the PI or designee and/or Sponsor.

The CRU will contact all subjects who received LOXO-292 (including subjects who terminate from the study early [ET]) at the EOS (as defined in the Study Events Flowchart, [Section 6](#)) by a follow up phone call (FU). The EOS/FU phone call will be performed 7 days (\pm 2 days) after EOT or ET (as defined in the Study Events Flowchart, [Section 6](#)) to determine if any SAE or study drug related AE has occurred since EOT or ET.

10.1.2 End of Study Definition

End of Study (EOS) is defined as the day on which the subject completes the follow up phone call (Study Events Flow Chart, [Section 6](#)).

Study completion applies to the clinical conduct of the study overall (i.e., last subject's Follow-up phone call).

11 STUDY POPULATION

The Sponsor will review medical history and all screening evaluations for potential subjects prior to enrollment. The Sponsor will provide approval of subjects for enrollment prior to dosing.

11.1 Inclusion Criteria

Subjects must fulfill all of the following inclusion criteria to be eligible for participation in the study:

1. Healthy, adult, male or female (of non-childbearing potential only), 18-55 years of age, inclusive, at Screening.
2. Continuous non-smoker who has not used tobacco- and/or nicotine-containing products for at least 3 months prior to dosing and through EOT or ET.
3. Body mass index (BMI) ≥ 18.0 and $\leq 32.0 \text{ kg/m}^2$ at Screening and have a minimum weight of at least 50 kg at Screening.
4. Medically healthy with no clinically significant medical history, physical examination, laboratory profiles, vital signs or ECGs, as deemed by the PI or designee, and as confirmed by the Sponsor. Liver function tests (ALT and AST), serum (total and direct) bilirubin, amylase and lipase, and tests for hemoglobin, white blood cells (WBCs), and neutrophils must be within the upper limit of normal for the laboratory used by the clinical site at Screening and Check-in (Day -1). Rechecks of the liver function tests (ALT and AST), serum (total and direct) bilirubin, amylase and lipase, and tests for hemoglobin, WBCs, and neutrophils will be permitted up to two times to confirm subject eligibility. Subjects may be eligible for participation in the study based on rechecked values if the PI (or designee), with agreement from the Sponsor, feels that the results are not clinically significant, and will not impact study conduct.
5. A female of non-childbearing potential: must have undergone one of the following sterilization procedures at least 6 months prior to dosing:
 - hysteroscopic sterilization;
 - bilateral tubal ligation or bilateral salpingectomy;
 - hysterectomy;
 - bilateral oophorectomy;or be postmenopausal with amenorrhea for at least 1 year prior to dosing and follicle-stimulating hormone (FSH) serum levels consistent with postmenopausal status.
6. Males who are capable of fathering a child must agree to use one of the following methods of contraception from the time of the dose administration through 6 months after the last dose:

Male subjects will be surgically sterile for at least 90 days prior to Check-in (Day -1). If documentation is not available, male subjects must follow the contraception methods below:

- a. Male condom with spermicide, and
- b. For a female partner of male study participant:
 1. Intrauterine device (IUD) (hormonal IUD; e.g., Mirena®). Copper IUDs are acceptable (e.g., ParaGard®);
 2. Established use of oral, implanted, transdermal, or hormonal method of contraception associated with inhibition of ovulation; or
 3. Bilateral tubal ligation.

Males who practice true abstinence because of a lifestyle choice (i.e., do not become abstinent just for the purpose of study participation) are exempt from contraceptive requirements. Periodic abstinence by a female partner (e.g., calendar, ovulation, symptothermal, postovulation methods) and withdrawal are not acceptable methods of contraception. If a male subject is abstinent at the time of signing the informed consent form (ICF) but becomes sexually active during the study, he must agree to use contraception as described above.

Male subjects should ensure that condoms with spermicide are used from the time of the study drug administration until 6 months after the last dose of study drug when having intercourse with female partners who are pregnant or breast feeding. Male subjects are required to refrain from donation of sperm from Check-in (Day -1) until 6 months after the last dose of study drug.

For subjects who are exclusively in same-sex relationships, contraceptive requirements do not apply.

Males who have been sterilized, must have confirmed documentation of surgical success

7. Understands the study procedures in the ICF and be willing and able to comply with the protocol.

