Potential effects of LOXO-292 on the central nervous system were evaluated as part of the GLP 28-day repeat-dose study in rats, in functional observational battery tests and locomotor activity assessments. Findings were limited to animals receiving the high dose on week 4 of the dosing phase, and were attributed to poor general body condition and weight changes associated with LOXO-292 administration rather than specific neurological effects. Additionally, no microscopic abnormalities in neuronal tissues were found.

In toxicology studies of LOXO-292 that were conducted in the rat and minipig, the primary pathologic findings for both species were in the tongue, pancreas, bone marrow and lymphoid tissues; while the gastrointestinal tract and ovaries were target tissues in minipig. Other target tissues identified in the rat included: multi-tissue mineralization, physeal cartilage, incisor teeth, lung, Brunner's gland, and possibly liver. Assessment of doses

associated with moribundity/death revealed a steep dose response curve for both species. LOXO-292 was not mutagenic in the GLP bacterial mutation assay. When evaluated in two in vitro assays, LOXO-292 was not genotoxic. LOXO-292 was not found to be phototoxic when evaluated in an in vitro neutral red uptake phototoxicity assay.

Based on preclinical pharmacology experiments with human cancer cells in vitro and in murine xenograft models, meaningful inhibition of RET in tumors is expected to be achievable with oral dosing regimens ≥ 40 mg/day.

Based on the nonclinical profile, including results from animal toxicology studies, theoretical risks of human exposure to LOXO-292 include the following: loss of appetite, decrease in body weight, increase in total white blood cells, neutrophils, and monocytes, decrease in albumin, increase in globulin, decreased albumin:globulin ratio, decrease in total protein, increased body temperature, lethargy, increase in cholesterol and triglycerides, increase in phosphorus, changes in taste sensation and/or development of xerostomia, gastrointestinal symptoms/signs: nausea, vomiting, loose stools, abdominal discomfort, decreases in red cell mass (red blood cell [RBC], hemoglobin, hematocrit) and reticulocytes, decrease in platelets, increases in liver function tests (alkaline phosphatase, aspartate aminotransferase, and alanine aminotransferase) and possible pancreas injury.

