14.1 Sample Size Determination

The sample size chosen for this study was selected without statistical considerations. It has been determined adequate to meet the study objectives.

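### Inclusion criterion 4 gives hemoglobin only an upper limit, although the risk the protocol lists for hemoglobin is a decrease

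*Protocol*

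**What the plan says.** Criterion 4 in Section 11.1 of the Protocol has three parts.

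- A general health requirement: "Medically healthy with no clinically significant medical history, physical examination, laboratory profiles, vital signs or ECGs, as deemed by the PI or designee", with confirmation by the Sponsor.
- A numeric requirement on named tests. It begins with ALT, AST, bilirubin, amylase and lipase and goes on to the blood counts: "and tests for hemoglobin, white blood cells (WBCs), and neutrophils must be within the upper limit of normal". One limit and two time points serve for all of them: they "must be within the upper limit of normal for the laboratory used by the clinical site at Screening and Check-in (Day -1").
- A recheck provision. The named tests may be repeated up to twice to confirm eligibility. A subject may be accepted on rechecked values if the investigator, with the Sponsor's agreement, considers them not clinically significant.

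Section 11 adds a further step. The Sponsor reviews medical history and screening evaluations, and "The Sponsor will provide approval of subjects for enrollment prior to dosing".

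The Nonclinical part of Section 8.1.1 describes the hazards. In the animal studies, "the primary pathologic findings for both species were in the tongue, pancreas, bone marrow and lymphoid tissues". The list of theoretical human risks includes "decreases in red cell mass (red blood cell [RBC], hemoglobin, hematocrit) and reticulocytes, decrease in platelets", and for white cells "increase in total white blood cells, neutrophils, and monocytes".

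**The concern.** An upper limit suits tests whose feared change is a rise. Hemoglobin shares the same phrase, but the change listed for it is a fall. The stated limit would hold back a healthy volunteer with a high hemoglobin and says nothing about one with a low hemoglobin.

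Two things are at stake. The first is baseline safety: a subject who starts low has less reserve for a listed effect and for the planned blood draw, which Section 13.4 puts at 168 mL with up to 50 mL more if needed (168 + 50 = 218 mL). The second is clarity. The wording could be a merger of a two-sided normal-range rule and a one-sided upper-limit rule, and the site cannot tell which was meant for the counts.

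**Working it through.** No arithmetic applies. Section 14.1 states that "The sample size chosen for this study was selected without statistical considerations", and no power, error rate or event count depends on this criterion. The check is to set the limit beside the listed risk, test by test.

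| Test | Risk listed in Section 8.1.1 | Numeric limit in criterion 4 | Do they face the same way? |
|---|---|---|---|
| ALT, AST | Increase | Upper | Yes |
| Bilirubin | Not named | Upper | No conflict |
| Amylase, lipase | Not named; possible pancreas injury is listed | Upper | No conflict |
| White cells, neutrophils | Increase | Upper | Yes |
| Hemoglobin | Decrease | Upper | No |

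Hemoglobin is the only named test on which the two sections pull in opposite directions. The inclusion and exclusion criteria (Sections 11.1 and 11.2) contain no lower limit for hemoglobin, white cells or neutrophils.

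Next, follow a subject whose hemoglobin is below the laboratory's range at Check-in.

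1. Numeric sentence: the value does not exceed the upper limit, so the sentence is met.
2. Recheck: its stated purpose is to confirm eligibility. The numeric limit has not been breached, so nothing in the text calls for a repeat.
3. Sponsor agreement on rechecked values: this depends on step 2 and is not reached.
4. General health clause: the investigator, with Sponsor confirmation, may judge the value clinically significant and exclude the subject.
5. Sponsor approval under Section 11: this comes before dosing, but the material named for review is medical history and screening evaluations. Check-in values are not mentioned.

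A subject with hemoglobin above the range fails at step 1 and enters steps 2 and 3. The structured route therefore serves the direction that is not the listed risk.

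The protocol does write two-sided limits elsewhere: BMI from 18.0 to 32.0 kg/m² in inclusion criterion 3, diastolic and systolic pressure in exclusion criterion 13, and heart rate from 45 to 99 bpm in exclusion criterion 14.

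**The case against.** The strongest reply is that the numeric sentence is only one of several barriers. Every inclusion criterion must be met, and criterion 4 itself demands a laboratory profile free of clinically significant findings. Exclusion criteria 2 and 3 bar significant conditions and illnesses that add risk or confound results. Criteria 21 and 22 bar recent blood donation, significant blood loss and plasma donation. This stands. A reader might infer that subjects with low counts are simply admitted, and the documents do not support that: such values go to judgement. Judgement alone is not a full answer, however. It also covers ALT and lipase, for which the authors still added a numeric limit.

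A second reply is that the recheck provision lets the investigator and Sponsor accept out-of-range values anyway, so a two-sided limit would not be a firm barrier. That is also correct. The gain is a prompt to repeat the test and a required agreement, not an automatic exclusion.

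A third reply concerns white cells and neutrophils. A reader might extend the criticism to them, but their listed risk is an increase and the upper limit matches it. Any case for a lower bound rests only on the animal bone marrow finding, which is not itself an entry in the list of theoretical human risks.

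Finally, platelets are a listed decrease and have no numeric limit in criterion 4. That is an absent limit, not one facing the wrong way, and is outside this point. The sponsor may wish to consider it in the same edit.

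**Conclusion.** The point holds for hemoglobin: the only numeric limit is on the opposite side from the listed risk, and a low value does not bring the criterion's own recheck and agreement step into play. It is a modest defect in an eligibility rule that applies at Screening and Check-in to every subject, worth correcting because the correction is so small. The conclusion rests on taking the phrase literally. If the authors meant the normal range, the text should say so.

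Two larger claims might be inferred and are not supported.

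- A probability that someone with a low count is enrolled. The documents give no distribution of screening values. A figure built on an assumed reference interval would ignore the health clause and Sponsor approval, and one combining several counts could not treat them as independent, since neutrophils are part of the white cell count.
- A distortion of dose escalation. The specific triggers in Section 12.4.1 need drug-related toxicity of grade 3 or higher judged clinically significant, or a drug-related serious event. Nothing shows that a mildly low starting value would produce either. Hematology is taken at Check-in (Section 6), and differences from baseline are to be summarized where appropriate (Section 14.3.1), so a low starter would be visible.

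**What to change.** Reconcile Section 8.1.1 with criterion 4 by splitting the numeric sentence.

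- ALT, AST, total and direct bilirubin, amylase and lipase: keep the upper limit of normal.
- Hemoglobin: refer to the laboratory's normal range, so that the low side is covered too.
- White cells and neutrophils: keep the upper limit and state whether a lower bound is also intended. If it is not, say that low values are left to the investigator and Sponsor.
- Recheck and Sponsor-agreement provision: keep it as it is and make clear that it applies to a low hemoglobin.

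The cost is one reworded sentence and somewhat more rechecks or screen failures, softened by the two repeats already allowed. Sample size, endpoints and analyses are unaffected.

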11.2 Exclusion Criteria

Subjects must not be enrolled in the study if they meet any of the following criteria:

1. Is mentally or legally incapacitated or has significant emotional problems at the time of the Screening visit or expected during the conduct of the study.
2. History or presence of clinically significant medical or psychiatric condition or disease in the opinion of the PI or designee, and as confirmed by the Sponsor.

3. History of any illness that, in the opinion of the PI or designee, and as confirmed by the Sponsor, might confound the results of the study or poses an additional risk to the subject by their participation in the study.
4. History of gastritis, gastrointestinal tract, or hepatic disorder or other clinical condition that might, in the opinion of the PI or designee, and as confirmed by the Sponsor, affect the absorption, distribution, biotransformation, or excretion of LOXO-292.
5. History or presence of alcoholism or drug abuse within the past 2 years prior to dosing.
6. History or presence of hypersensitivity or idiosyncratic reaction to the study drugs or related compounds, or inactive ingredients.
7. History or presence of:
 - liver disease,
 - pancreatitis,
 - peptic ulcer disease,
 - intestinal malabsorption,
 - gastric reduction surgery,
 - history or presence of clinically significant cardiovascular disease:
 - myocardial infarction or cerebrovascular thromboembolism within 6 months prior to dosing
 - symptomatic angina pectoris
 - New York Heart Association Class ≥ 2 congestive heart failure
 - congenital prolonged QT syndrome
 - ventricular pre-excitation syndrome (Wolff-Parkinson White syndrome)
 - arrhythmia or history of arrhythmia requiring medical intervention
 - ventricular dysfunction or risk factors for Torsades de Pointes (e.g., heart failure, cardiomyopathy, family history of Long QT Syndrome)
 - significant screening ECG abnormalities:
 - left bundle-branch block
 - second degree atrioventricular (AV) block, type 2, or third-degree AV block
 - Frederica corrected QTc (QTcF) interval is >450 msec
 - ECG findings deemed abnormal with clinical significance by the PI or designee at Screening and prior to dosing.
8. Female subjects of childbearing potential.
9. Female subjects with a positive pregnancy test or who are lactating.

10. Positive urine drug or alcohol results at Screening or Check-in (Day -1).
11. Positive urine cotinine test at Screening or Check-in (Day -1).
12. Positive results at Screening for human immunodeficiency virus (HIV), hepatitis B surface antigen (HBsAg) or hepatitis C virus (HCV). Subjects who are positive for hepatitis B virus, HCV, or HIV by antibody will require confirmation by polymerase chain reaction (PCR) before enrollment to detect presence of active virus. Subjects who are PCR positive will not be eligible.
13. Subjects with at-rest (i.e., supine for at least 5 minutes) diastolic BP of <50 or >89 mmHg and/or supine systolic BP of <89 or >139 mmHg at Screening, Check-in (Day -1), and prior to dosing. Rechecks of blood pressure values will be permitted up to two times to confirm eligibility for study participation. Subjects may be eligible for participation in the study based on rechecked values if the PI (or designee), with agreement from the Sponsor, feels that the results are not clinically significant, and will not impact study conduct.
14. Supine heart rate is lower than 45 bpm or higher than 99 bpm at Screening, Check-in (Day -1), and prior to dosing. Rechecks of heart rate values will be permitted up to two times to confirm eligibility for study participation. Subjects may be eligible for participation in the study based on rechecked values if the PI (or designee), with agreement from the Sponsor, feels that the results are not clinically significant, and will not impact study conduct.
15. Estimated creatinine clearance <90 mL/min at Screening or Check-in (Day -1).
16. Unable to refrain from or anticipates the use of any drug, including prescription and non-prescription medications, herbal remedies, or natural or vitamin supplements for 14 days prior to dosing and through EOT or ET, unless allowed by the PI (or designee), with agreement from the Sponsor. Hormone replacement therapy (HRT) is not permitted. After dosing, acetaminophen (up to 2 g per 24 hours) may be administered at the discretion of the PI or designee.
17. Unable to refrain from or anticipates the use of any inhibitor or inducer of CYP3A4/A5 or of P-gp for 28 days prior to dosing and through EOT or ET. Appropriate sources (e.g., Flockhart TableTM) will be consulted to confirm lack of PK interaction with study drug.
18. Unable to refrain from or anticipates the use of proton pump inhibitors, antacids and H2-receptor antagonists for 14 days prior to dosing and through EOT or ET.
19. Unable to refrain from or anticipates the use of any drugs that prolongs the QT/QTc interval for 14 days prior to dosing and through EOT or ET.
20. Has been on a diet incompatible with the on-study diet, in the opinion of the PI or designee, and as confirmed by the Sponsor, within the 30 days prior to dosing and through EOT or ET.
21. Donation of blood or significant blood loss within 56 days prior to dosing.

22. Plasma donation within 7 days prior to dosing.
23. Poor peripheral venous access.
24. Participation in previous investigational trial with LOXO-292.
25. Strenuous exercise within 5 days prior to Check-in (Day -1).
26. Dosing in any other investigational study drug trial involving administration of any investigational drug in the past 30 days or 5 half-lives (if known), whichever is longer, prior to dosing.

